We will recruit a novel sample (n = 120) parent/child dyads (children 36 - 72 months of age) referred for evaluation of ASD or developmental delays. These children and a primary caregiver will participate in a home-based tele-assessment session and a subsequent blinded in-person evaluation. We will again include English/Spanish speaking families with access to a device that will support Zoom.

Inclusion/Exclusion Criteria: Aim 3

Inclusion

- English/Spanish Speaking families
- Children 36-72 months of age
- access to a device capable of supporting Zoom
- has not participated in a diagnostic evaluation

-Exclusion

- severe sensorimotor impairments

Study Procedures

Initial deployment, evaluation, and refinement of the TAP-Preschool:

Consenting families will be scheduled for a single tele-assessment session with a consented licensed psychologist ("remote clinician") from our clinical research center

(n=10). This clinician will coach parents through the TAP-Preschool procedures. Although families will receive standard, basic support regarding tele-assessment procedures, they will not receive extensive training on the TAP-P prior to the session in order to mimic real-world use. All remote clinicians will be experts in ASD with training on the original TAP and ADOS-2 research reliability. Each clinician will participate in 3 sessions (2 children with ASD, 1 other developmental concerns). Clinicians will be blinded to child diagnostic status. Participating telemedicine clinicians in this aim will not be aware of the ratio (2:1 ASD vs. other DD) or recruitment status prior to evaluation ratings. As children will have existing diagnoses, no diagnostic feedback will be provided.

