If a clinician thinks that the child appears to be too distressed to complete the evaluation, opportunities will be given to reschedule the assessment. If the parent declines, the clinician will note that the child was unable to complete the assessment and only data obtained will be included in the study while also routing families to appropriate clinical referral pathways.

Statistical Design and Power

In Specific Aim 2, we will collect user data (caregiver, clinicians) on satisfaction, ease of implementation, and diagnostic certainty (clinicians only). We will examine these data

descriptively (frequencies for satisfaction items; mean/SD for diagnostic certainty) and use them to inform modifications to TAP-P procedures.

In Specific Aim 3, we will benchmark acceptability/usability and preliminary clinical value and then perform rigorous evaluation of the TAP-Preschool relative to in-person evaluation. Our sample size has been determined to power primary analyses around estimates of accuracy, specific psychometric properties, as well as family experience. We will use receiver operating characteristic (ROC) curve analyses to determine a cut score for the optimal scoring method and evaluate characteristics utilizing the entire sample. We will examine agreements and corresponding sensitivity, specificity, and positive and negative predictive value. After estimated attrition of approximately 10%, 108 subjects (projected 65 ASD; 43 non-ASD) will be available for analysis. PPV and sensitivity will have a margin of error no larger than +/- 9.7%, and NPV and specificity will have a margin of error no larger than +/- 12.0%. Margin of error (half the width of a 95% confidence interval) calculations are based on preliminary data from prior data from tele-assessment of ASD and conservatively assuming 80% PPV and 80% NPV. For inter-rater and test-retest reliability, we will be able to measure percent agreement with a margin of error no larger than +/- 7.5% and Cohen's kappa within +/- 0.12. For estimating associations among factors potentially related to clinician diagnostic certainty and caregiver satisfaction, we will have 80% power to detect odds ratios larger than 1.37. All calculations use a two-sided significance level of 0.05 (See Statistical Design and Power for more detail).

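### At the plan's stated 80% PPV and 80% NPV, the ±12.0% limit fails for both NPV (±13.1%) and specificity (±14.1%)

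*Combined protocol and SAP*

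**What the plan says.** Aim 3 of the combined protocol and SAP enrols 120 parent/child dyads ("We will recruit a novel sample (n = 120) parent/child dyads"). The Statistical Design and Power section allows about 10% attrition and expects that "108 subjects (projected 65 ASD; 43 non-ASD) will be available for analysis". The accuracy analysis uses ROC curves to "determine a cut score for the optimal scoring method and evaluate characteristics utilizing the entire sample", and then reports sensitivity, specificity, PPV and NPV.

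The same section says the sample size was chosen to support these accuracy estimates, and gives two upper limits on their precision:

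- "PPV and sensitivity will have a margin of error no larger than +/- 9.7" percent;
- "NPV and specificity will have a margin of error no larger than +/- 12.0" percent.

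It defines the margin as half the width of a 95% confidence interval. The calculations are said to draw on earlier tele-assessment data, "conservatively assuming 80% PPV and 80% NPV". No sensitivity, specificity, or count of test positives and negatives is given. The text points to a fuller account of design and power, which is not in the document.

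**The concern.** One limit is given for PPV and sensitivity together, and one for NPV and specificity together. The two measures in each pair do not share a denominator. Sensitivity is a proportion of children with ASD and specificity of children without ASD. PPV is a proportion of test positives and NPV of test negatives. A single cut score applied to the whole sample produces one 2x2 table, so the four measures and their denominators are tied together and cannot be set independently.

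At stake is the precision quoted for two of the four accuracy measures: how far a negative result can be trusted, and how often children without ASD are classified as having it. There is also an undisclosed implication. At 65/43, assuming 80% for both predictive values means assuming specificity near 66%, so about one in three non-ASD children would test positive.

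**Working it through.** **Inputs** (all from Statistical Design and Power): 108 analysed children (120 × 0.9), 65 ASD and 43 non-ASD; PPV = NPV = 0.80; margin = 1.96 × √(p(1 − p)/n).

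**1. The plan's own figures reproduce.**

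- p = 0.80, n = 65: 1.96 × √(0.16/65) = 0.0972, the stated 9.7%.
- p = 0.80, n = 43: 1.96 × √(0.16/43) = 0.1196, the stated 12.0%.

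So 80% was applied to all four measures, with 65 and 43 as the denominators throughout.

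**2. The table implied by the stated assumptions.** Let P be the number of test positives. Children with ASD are the true positives plus the false negatives:

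0.8P + 0.2(108 − P) = 65, so 0.6P = 43.4 and P = 72.33. Test negatives = 108 − 72.33 = 35.67.

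| | ASD | Non-ASD | Total |
|---|---|---|---|
| Test positive | 57.87 | 14.47 | 72.33 |
| Test negative | 7.13 | 28.53 | 35.67 |
| Total | 65 | 43 | 108 |

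Sensitivity = 57.87/65 = 89.0%. Specificity = 28.53/43 = 66.4%.

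**3. Each margin on its own denominator.**

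| Measure | Value | n | Calculation | Margin | Stated limit |
|---|---|---|---|---|---|
| PPV | 80% | 72.33 | 1.96 × √(0.16/72.33) | ±9.2% | ±9.7% |
| Sensitivity | 89.0% | 65 | 1.96 × √(0.890 × 0.110/65) | ±7.6% | ±9.7% |
| NPV | 80% | 35.67 | 1.96 × √(0.16/35.67) | **±13.1%** | ±12.0% |
| Specificity | 66.4% | 43 | 1.96 × √(0.664 × 0.336/43) | **±14.1%** | ±12.0% |

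**4. Sensitivity of the result.**

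- *Whole children.* With 58 true positives, 7 false negatives, 14 false positives and 29 true negatives, PPV = 58/72 and NPV = 29/36, both 80.6%. The margins are NPV ±12.9% and specificity (29/43 = 67.4%) ±14.0%.
- *Interval method.* For the table in step 2, NPV and specificity are ±12.8% and ±13.6% (Wilson), ±13.1% and ±13.7% (Agresti-Coull), ±14.1% and ±14.8% (Clopper-Pearson). All exceed 12.0%.
- *If 65/43 were test positives and negatives.* NPV is ±12.0%, but non-ASD children number 108 − (0.8 × 65 + 0.2 × 43) = 47.4. Specificity is then 34.4/47.4 = 72.6%, ±12.7%.
- *If 80% were sensitivity and specificity.* Specificity is ±12.0%, but test negatives number 47.4 and NPV is 34.4/47.4 = 72.6%, ±12.7%.

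**5. Where the limit does hold.** With NPV at 80%, PPV must reach about 86.4% for the NPV margin to fall to 12.0%, and about 86.7% for the specificity margin. With PPV = NPV, the thresholds are about 83.1% and 87.4%.

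**6. Scale.** At 80%/80% and the same case mix, ±12.0% for NPV needs 0.16 × (1.96/0.12)² = 42.7 test negatives, or 42.7 ÷ (35.67/108), about 130 analysed children. For specificity it needs 0.664 × 0.336 × (1.96/0.12)² = 59.6 non-ASD children, or 59.6 ÷ (43/108), about 150. The plan has 108.

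**The case against.** The best defence reads 80% as a minimum for all four measures. The wording is that of an upper limit under a cautious assumption, and the published figures are exactly what 80% on 65 and on 43 gives. If sensitivity, specificity, PPV and NPV are each at least 80% at 65/43, the largest margins are 12.0% for NPV and for specificity, 9.0% for sensitivity and 8.2% for PPV. Both limits then hold. The 12.0% is reached where NPV and specificity are both 80%, which makes test negatives exactly 43. On this view the 66.4% specificity is derived by the reader and is nowhere in the plan.

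The arithmetic of that defence is right, but it needs a floor on specificity that the plan does not write. The text names 80% only for PPV and NPV. A floor on those two alone does not rescue the limit: the 58/7/14/29 table in the working satisfies it with NPV at ±12.9%. So does a table with 64 true positives, 1 false negative, 16 false positives and 27 true negatives (PPV 64/80 = 80%, NPV 27/28 = 96.4%), where specificity is 27/43 = 62.8%, ±14.4%.

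Three other points stand in part. The fuller power account may state the missing values; it could make the limit conditional on them, but could not make it true at 65/43 with 80%/80%. The excess is small, and the 65/43 split is itself a projection: with 38 non-ASD children the plan's own formula already gives 1.96 × √(0.16/38) = 12.7%. And ±12.0% is not stated as a design target, so the sizes of 130 and 150 show scale only and are not a shortfall in recruitment.

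**Conclusion.** The concern holds. At 65 ASD, 43 non-ASD and 80% for both predictive values, the stated upper limit of ±12.0% is exceeded by 1.1 points for NPV (±13.1%) and 2.1 points for specificity (±14.1%). The ±9.7% limit for PPV and sensitivity holds with room to spare.

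This rests on taking 65/43 as the diagnosis on the in-person evaluation, which is the plain meaning of ASD and non-ASD, and on taking the only accuracy values the plan states. Neither alternative reading of those inputs tested in the working brings both measures within 12.0%. The limit is correct if accuracy is sufficiently higher than assumed, but an upper limit ought to hold at the case the plan itself calls conservative. The consequence is modest: no test or decision rule is tied to these margins, and the final intervals will use the observed counts.

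**What to change.** In Statistical Design and Power, state the assumed sensitivity and specificity and the projected numbers of test positives and test negatives, and derive all four margins from that one table. There are two ways to do this:

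- Keep PPV = NPV = 80% and report PPV ±9.2%, sensitivity ±7.6%, NPV ±13.1% and specificity ±14.1%, noting the implied 66.4% specificity.
- If the earlier tele-assessment data support better performance, state those values and show that the limits hold there. For example, NPV and specificity of 80% with PPV and sensitivity of about 87% would do.

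Unless a floor on all four measures is stated, describe the margins as approximate under the stated assumptions and drop the claim of a maximum.

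The cost is a change of numbers and wording. Enrolment stays at 120 and no procedure changes. Under the first option the quoted NPV and specificity precision become slightly less favourable. If the fuller power account already contains the assumed table, it need only be copied here and the figures corrected to match.

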All consented families will complete an initial home-based tele-assessment visit via Zoom that includes the TAP-Preschool and a brief symptom-focused developmental interview with a consented clinician. The initial tele-assessment session includes interviewing and developmental assessment to mimic real-world use of TAP-Preschool. The visit is designed to take less than 90 minutes, with TAP-Preschool evaluation lasting <30 minutes. Although we will not limit length, we will time all sessions. After the session, the examiner will record the clinical diagnosis issued (ASD, other developmental concerns, or typical development) and complete two diagnostic certainty ratings, one dichotomous, the other continuous. All initial TAP-Preschool administrations will be recorded via Zoom, and 50% of administrations (randomly selected) will be co-scored by a blinded examiner, unaware of prior assessment results and diagnostic decision, to

evaluate inter-rater reliability. Within 7 days of the remote assessment, families will participate in an in-person diagnostic assessment including common comprehensive measures of ASD, cognitive skills, and adaptive behavior. We will randomly select 25% of families to participate in a remote home-based re-test with TAP-Preschool two weeks following initial administration.

Tele-assessment measures: Prior to the appointment, caregivers will complete a Demographics Questionnaire (i.e., age, gender, race/ethnicity, zip code, parent education) and a Medical History Form through a secure HIPAA-compliant web portal (REDCap). To reduce technology-related disruptions, research staff will talk to families before the visit about connectivity settings and recommended materials.

These will take approximately 20 minutes to complete.

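### One precision bound (±7.5% agreement, ±0.12 kappa) is claimed for both reliability analyses, but with only 27-30 families re-tested the test-retest agreement margin is about 1.4 to 2 times wider at 80-90% agreement.

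*Combined protocol and SAP*

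**What the plan says.** The precision claim is in Statistical Design and Power. One sentence covers both reliability analyses: "For inter-rater and test-retest reliability, we will be able to measure percent agreement with a margin of error no larger than +/- 7.5" per cent, and Cohen's "kappa within +/- 0.12". The same section defines the margin of error as half the width of a 95% confidence interval. It expects "108 subjects (projected 65 ASD; 43 non-ASD) will be available for analysis", and it says "Our sample size has been determined to power primary analyses around estimates of accuracy, specific psychometric properties". The only planning proportion it gives is for predictive values: "conservatively assuming 80% PPV and 80% NPV". It gives no expected agreement and no expected kappa for reliability.

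The sample sizes for the two analyses come from elsewhere. Under Specific Aim 3, "We will recruit a novel sample (n = 120) parent/child dyads". The section on the assessment of the TAP-Preschool in the novel sample says that "50% of administrations (randomly selected) will be co-scored by a blinded examiner", for inter-rater reliability. For test-retest it says: "We will randomly select 25% of families to participate in a remote home-based re-test with TAP-Preschool two weeks following initial administration".

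**The concern.** A bound worded as a maximum, and given once for two analyses, has to hold for the smaller of them. The re-test subsample is half the size of the co-scored one. At any common agreement rate, its margin is therefore √2 = 1.41 times as wide. If ±7.5% and ±0.12 describe inter-rater reliability, test-retest comes to about ±10.6% (7.5 × 1.41) and ±0.17 (0.12 × 1.41), whatever agreement rate was assumed.

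The plan counts psychometric properties among the analyses that the sample size was set to support, and stability on re-test is a basic property of a new diagnostic tool. A reader who accepts ±7.5% will expect the re-test substudy to separate moderate from high stability. With about 27 families it may not. The exact 95% interval is 62-94% if 22 of 27 agree and 71-98% if 24 of 27 agree.

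**Working it through.** **Inputs from the plan.** 120 enrolled, 108 analysable (65 ASD, 43 non-ASD), 50% co-scored, 25% re-tested, 95% two-sided intervals.

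- Inter-rater: 0.50 × 108 = 54, or 0.50 × 120 = 60.
- Test-retest: 0.25 × 108 = 27, or 0.25 × 120 = 30.

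**Assumptions.** One agreement outcome per child. Agreement rates of 80%, 90% and 95% are shown because the plan states none for reliability.

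**Step 1: reproduce the plan's own margins.** Half-width = 1.96 × √(p(1−p)/n).

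- p = 0.80, n = 65: 9.72% (plan: 9.7%).
- p = 0.80, n = 43: 11.96% (plan: 12.0%).

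Both match, so this is very likely the formula the plan used.

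**Step 2: apply it to percent agreement (stated bound ±7.5%).**

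| Agreement | n=27 | n=30 | n=54 | n=60 | n=108 |
|---|---|---|---|---|---|
| 80% | 15.09% | 14.31% | 10.67% | 10.12% | 7.54% |
| 90% | 11.32% | 10.74% | 8.00% | 7.59% | 5.66% |
| 95% | 8.22% | 7.80% | 5.81% | 5.51% | 4.11% |

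For test-retest at 80-90% agreement, the ratio to 7.5% runs from 10.74/7.5 = 1.43 to 15.09/7.5 = 2.01. Wilson and exact intervals do not rescue the bound: for the same sizes and rates their half-widths are 11.1-14.3% and 12.2-15.9%.

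**Step 3: what would make ±7.5% true.** Solving the formula for p gives a minimum agreement of 95.9% (n=27), 95.4% (n=30), 91.3% (n=54), 90.3% (n=60) or 80.3% (n=108). In whole families, no more than one re-test may disagree: 25/27 gives ±9.9% and 28/30 gives ±8.9%, while 26/27 gives ±7.1%. Solving for n gives 109.3 re-tests at 80% and 61.5 at 90%, so about 110 and 62.

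**Step 4: where 7.5% may have come from.** At 80%, the plan's only stated rate, it matches all 108 children (7.54%). At 90% it is nearly met by 60 co-scored administrations (7.59%). The plan does not say which was used, if either. The bound fails for test-retest at both rates.

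**Step 5: kappa (stated ±0.12).** Half-width of kappa ≈ agreement half-width / (1 − chance agreement). Three values of chance agreement are shown:

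- 0.375, implied by the plan's two figures: 1 − 0.075/0.12.
- 0.44, the minimum for three diagnoses with 65/108 = 0.602 ASD and equal rater marginals: 0.602² + 2 × 0.199².
- 0.52, two categories with that mix: 0.602² + 0.398².

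| Agreement | Chance | n=27 | n=30 | n=54 | n=60 |
|---|---|---|---|---|---|
| 80% | 0.375 | 0.241 | 0.229 | 0.171 | 0.162 |
| 80% | 0.44 | 0.269 | 0.256 | 0.191 | 0.181 |
| 80% | 0.52 | 0.314 | 0.298 | 0.222 | 0.211 |
| 90% | 0.375 | 0.181 | 0.172 | 0.128 | 0.121 |
| 90% | 0.44 | 0.202 | 0.192 | 0.143 | 0.136 |
| 90% | 0.52 | 0.236 | 0.224 | 0.167 | 0.158 |
| 95% | 0.375 | 0.132 | 0.125 | 0.093 | 0.088 |
| 95% | 0.52 | 0.171 | 0.162 | 0.121 | 0.115 |

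No test-retest entry is 0.12 or less. Reaching 0.12 there needs agreement of 95.4-95.9% with chance agreement 0.375, or 97.3-97.6% with 0.52. Kappa does not reveal the sample size used: with chance agreement 0.375, n=108 at 80% (0.0754/0.625) and n=60 at 90% (0.0759/0.625) both give 0.121.

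**The case against.** The strongest reply is that the size of the shortfall depends on an agreement rate the plan never gives. The accuracy margins are said to rest on the team's preliminary tele-assessment data, which the documents do not report, and the section points to further power detail. If the team expected about 95.4% agreement on 30 re-tests, ±7.5% would be the worse of the two margins (inter-rater with n=60 would be ±5.3%) and the agreement part of the sentence would be true for both analyses. One bound for two analyses is not wrong in itself, and the √2 step starts by assigning 7.5% to inter-rater. This stands as a limit on the ratio: 1.4 to 2 holds for 80-90% agreement, not for every rate. It does not support the bound, because agreement of 95-96% is nowhere stated and would be an optimistic planning value beside a conservative 80%.

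The unit of agreement is also unstated. Pooling item scores would raise the nominal count, but no such analysis is described, and items within a child are correlated.

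A chance agreement of 0.375 is open to challenge too. It is back-calculated from the two disputed figures and lies below the 0.44 that the projected case mix allows for per-child diagnosis with equal marginals. That is a fair criticism, but it makes the kappa shortfall larger: with 0.44-0.52, test-retest at 80-90% agreement is about ±0.19 to ±0.31.

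Finally, no decision rule or enrolment number depends on 7.5% or 0.12. That limits the seriousness of the point but does not make the statement correct.

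**Conclusion.** The concern holds. The plan's single bound is not delivered by its 25% re-test subsample unless agreement is about 95-96% or higher. At 80-90% agreement the test-retest margin is ±10.7% to ±15.1%, which is 1.43 to 2.01 times the stated figure. Test-retest kappa is ±0.17 to ±0.31 over chance agreement 0.375-0.52. Inter-rater precision also falls short at 80% (±10.1-10.7%) and only comes close at 90% (±7.6-8.0%), so the problem is not confined to test-retest.

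These figures assume one outcome per child, 27-30 re-tests and 54-60 co-scored administrations, and the plan's own interval formula. The kappa figures also rest on the chance-agreement values shown. Confidence is high that the bound is unsupported for test-retest as written; the exact ratio depends on the assumed agreement. It should be fixed, because it misstates the precision of a property the sample size is said to support. The accuracy margins stand.

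**What to change.** Replace the single reliability sentence with two, each giving its sample size, unit of agreement (diagnosis, cut score or item), assumed agreement and assumed chance agreement. Using the analysable sample, one outcome per child and chance agreement of 0.44-0.52 from the projected case mix, they would read:

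- **Inter-rater, about 54 co-scored:** agreement ±10.7% at 80% or ±8.0% at 90%; kappa ±0.19-0.22 or ±0.14-0.17.
- **Test-retest, about 27 families:** agreement ±15.1% at 80% or ±11.3% at 90%; kappa ±0.27-0.31 or ±0.20-0.24.

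If the team's prior data point to other agreement or chance-agreement values, state them and recompute; with chance agreement 0.375 the lower ends fall to 0.17 and 0.13 for inter-rater and 0.24 and 0.18 for test-retest. Do not claim ±7.5% for test-retest unless those data support agreement of about 96%. For ±0.12 the requirement is the same with chance agreement 0.375 and rises to 97-98% with 0.52.

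The cost is a wording change and less favourable stated figures, with no added children or procedures. Keeping ±7.5% for test-retest by enlarging the subsample would need about 110 re-tests at 80% agreement or 62 at 90%, against 27-30 planned.

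### The single pair of reliability margins fits the full 108 children, not the roughly 54 co-scored and 27 re-tested; restate the margins for each sample and add a score-level ICC beside kappa

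*Combined protocol and SAP*

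**What the plan says.** In Statistical Design and Power, one sentence covers both reliability studies: "we will be able to measure percent agreement with a margin of error no larger than +/- 7.5" percent, with kappa within 0.12. It gives no assumed agreement rate and no number of children. The analysable total in the same paragraph is "108 subjects (projected 65 ASD; 43 non-ASD) will be available for analysis", from an enrolment described under Specific Aim 3 as "We will recruit a novel sample (n = 120) parent/child dyads".

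The reliability data come from subsamples set out in Study Procedures for the novel sample. For inter-rater reliability, "50% of administrations (randomly selected) will be co-scored by a blinded examiner". For test-retest, "We will randomly select 25% of families to participate in a remote home-based re-test with TAP-Preschool".

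The accuracy analysis will use ROC "curve analyses to determine a cut score for the optimal scoring method". This implies that the tool yields values that can be ordered. Percent agreement and kappa are the only reliability statistics named in the supplied text. No ICC, weighted kappa or other score-level measure appears.

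**The concern.** Two samples that differ in size by a factor of two cannot share one margin unless that margin is the worse of the two. The wording promises an upper bound for both, so it should hold for the smaller re-test sample. If it was worked out on the whole cohort, the sponsor is promising precision that the reliability data will not deliver, and readers may take the re-test result as firmer than it is.

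A second, smaller matter is the choice of statistic. If agreement and kappa are taken on the class at the cut, they use only the side of the line on which each paired score falls. They then depend on the share of children with ASD and on a threshold chosen in the same cohort. They describe reproducibility of the classification, not of the score. With only 27 re-test pairs, it is worth using the score as well.

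**Working it through.** **Inputs from the documents.** 120 enrolled; 108 analysable (65 ASD, 43 non-ASD, so about 60:40); 50% co-scored, 54 of 108 (60 of 120 without attrition); 25% re-tested, 27 of 108 (30 of 120). Margin of error is defined as half of a 95% interval, and "All calculations use a two-sided significance level of 0.05", so z = 1.96.

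**Assumptions.** No agreement rate is stated for reliability, so I use 80%, 90% and 95%. The 80% is the value that the same paragraph assumes for PPV and NPV. For kappa I take both ratings to be 60:40.

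**Check of the method.** Half-width = 1.96 × √(p(1−p)/n). With p = 0.80, n = 65 gives 9.72 points and n = 43 gives 11.96. These reproduce the plan's 9.7 and 12.0, so this is very likely the formula used.

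**The plan's 7.5.** With p = 0.80 and n = 108: 1.96 × √(0.16/108) = 7.54 points. The figure matches the full cohort at 80%.

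**Kappa.** Chance agreement pe = 0.6² + 0.4² = 0.52. Kappa = (po − 0.52)/0.48, which is 0.58 at 80%, 0.79 at 90% and 0.90 at 95%. Half-width = 1.96 × √(po(1−po)/n)/0.48. The fuller large-sample standard error agrees within 0.001.

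| Children | Agreement | Margin, points | Margin, kappa |
|---|---|---|---|
| 108 | 80% | 7.5 | 0.16 |
| 108 | 90% | 5.7 | 0.12 |
| 54 | 80% | 10.7 | 0.22 |
| 54 | 90% | 8.0 | 0.17 |
| 54 | 95% | 5.8 | 0.12 |
| 27 | 80% | 15.1 | 0.31 |
| 27 | 90% | 11.3 | 0.24 |
| 27 | 95% | 8.2 | 0.17 |

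Without attrition, 80% agreement gives 10.1 points (n = 60) and 14.3 points (n = 30). At n = 30 even 95% agreement gives 7.8 points and 0.16.

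**What the stated margins would require.** A margin of 7.5 points needs agreement of at least 91.3% with 54 children and 95.9% with 27. For the re-test that means at most one discordant child: 26/27 gives 1.96 × √(0.963 × 0.037/27) = 7.1 points, and 25/27 gives 9.9. With 26/27 the kappa margin is still 0.071/0.48 = 0.15. The kappa figure of 0.12 appears with 108 children at 90% agreement (0.118) or 54 at 95% (0.121). At n = 108 the two stated margins therefore point to different agreement rates.

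**ICC on the score.** ICC values are assumptions. For two ratings per child, the exact one-way interval uses F = (1+r)/(1−r), divided by the 97.5% F quantile on (n−1, n) degrees of freedom for the lower limit and multiplied by that on (n, n−1) for the upper. Each result is converted back by (F−1)/(F+1).
- r = 0.80 gives F = 9.
- n = 27: 9/2.171 = 4.145 and 9 × 2.184 = 19.66, so the 95% CI is 0.61 to 0.90 (half-width 0.15).
- n = 54: 9/1.718 = 5.239 and 9 × 1.720 = 15.48, so 0.68 to 0.88 (half-width 0.10).
- At r = 0.60 and n = 27 the half-width is 0.25.

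**The case against.** The sentence states expected precision and need not list every reliability analysis. It also points to a fuller power text that is not in the supplied document. The object of rating is not stated: agreement could be on items, on the class at the cut, or on the clinician's three-category diagnosis. The item scale and total range are not given, and who administers the re-test is not described. For a tool meant to support diagnosis, the reliability of the classification is directly relevant. These points stand, and they limit the ICC part to an addition that depends on there being a total score.

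A reader might infer four stronger things that the documents do not support.
- **That the re-test is almost uninformative.** With 27 children, agreement is still bounded to about 11 to 15 points. Kappa of 0.79 with a margin of 0.24 has a lower limit near 0.55. That is weak, but it is informative.
- **That an ICC is narrower than kappa by some fixed percentage.** They are different quantities. For a bivariate normal score cut at 60% positive, an ICC of 0.80 corresponds to a kappa of about 0.59, so comparing the two at one numerical value measures nothing.
- **That kappa should give way to the ICC.** That is a preference. Kappa answers the question about classification.
- **That the plan discards score information.** This follows only if kappa is taken on the dichotomised score, which is not stated.

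A sponsor could also reply that agreement will be high. For the co-scored sample, about 95% agreement does meet both margins after rounding. For the re-test, 95% misses both. None of these objections touches the mismatch between the margins and the sample sizes.

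**Conclusion.** The stated margins do not hold for the samples that supply the reliability data unless agreement is very high. At the 80% rate that reproduces the plan's own figure, the percent-agreement margin is understated by about 3 points for inter-rater (10.7 against 7.5) and is about twice the stated value for test-retest (15.1 against 7.5). The kappa margin is 0.22 and 0.31 against 0.12. At 90% agreement the excess is small for co-scoring in points (8.0) but remains clear for the re-test (11.3 points, 0.24).

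This rests on 10% attrition applied evenly to the subsamples, a 60:40 split in both ratings, and large-sample intervals. Removing attrition does not change the conclusion.

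A score-level ICC is a worthwhile addition, conditional on TAP-Preschool having a total score. It tightens what 27 pairs can say but leaves a wide interval if reliability is only moderate. The point is minor: it concerns a precision statement and an extra analysis, and it does not touch the accuracy estimates.

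**What to change.** 1. In Statistical Design and Power, replace the joint sentence with separate margins for the co-scored and re-test samples, each with its number of children, assumed agreement rate and ASD share. The table above supplies the values.
2. State what agreement and kappa are computed on (items, class at the cut, or diagnosis), and whether kappa is weighted.
3. Add an absolute-agreement ICC of the TAP-Preschool total score with 95% CI for both studies, and the within-child SD of paired scores. Choose the model to match the actual rater design: a two-way form suits a fixed or sampled panel that scores all the children, and a one-way form suits raters who vary from child to child. Keep percent agreement and kappa for the classification.

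The cost is SAP wording and one further model on paired scores already to be collected. No extra children, visits or co-scoring are needed. If the sponsor wants the stated margins themselves at moderate agreement, that would need larger subsamples, which is a separate decision with a real cost.
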